Aim 1: Determine whether interdisciplinary outpatient palliative care for PD and APD improves patient quality of life (QOL) and caregiver burden as compared to usual care including a neurologist. We will randomize 300 PD and APD patients from 3 sites who are at high risk for poor outcomes in a 1:1 ratio to either: a) Usual care or b) Usual care augmented by an outpatient interdisciplinary palliative care team. Data regarding patient symptoms, QOL and caregiver burden will be measured at baseline, 3, 6, 9 and 12 months. Our primary outcomes will be differences between groups in patient QOL and caregiver burden at 6 months. We will also examine patient symptom burden, spiritual wellbeing and mood as planned secondary outcomes. We *predict* that patient QOL and caregiver burden will be significantly improved in the palliative care group versus usual care at 6 months and that this difference will persist and widen by 12 months.

Aim 2: Describe the effects of an interdisciplinary outpatient palliative care intervention on patient and caregiver costs and service utilization. Data regarding health-related costs, including informal caregiver time, and the use of health and social services for the three months prior to each study visit will be assessed for all participants from Aim 1 using a standard schedule. Our primary outcome will be the difference between groups in total patients and caregiver costs from month 0 to month 6 of the study. Secondary analyses will

examine changes in healthcare utilization and cost from a systems perspective. We *predict* patient/caregiver costs will be lower for the palliative care group versus usual care at 6 months and that service utilization will shift towards home services and away from acute care such as emergency room visits and hospitalizations.

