- 3) Describe the impact of outpatient palliative care on cost and service utilization from a patient and caregiver perspective. As opposed to traditional cost-effectiveness analyses, these analyses do not depend on assumptions valuing quality of life years or other complex modeling. Rather they are designed to provide practical data directly relevant to patients, caregivers and PD advocacy groups.
- 4) Include patients with and without PD-related dementia (PDD) in a randomized clinical trial. One of the challenges of building a palliative care model for PD is the wide variability of clinical phenotypes, including a wide range of cognitive abilities and impairment. Our goal is to strive for inclusivity, specifically including PDD patients who are often excluded from clinical research but represent a very high-risk population for palliative care needs. We have specifically chosen primary outcome measures not dependent on cognitive status.
- 5) Use the Quality of Life: Alzheimer's Disease (QOL-AD)³⁹ and recently developed Edmonton Symptom Assessment Scale – Parkinson's Disease (ESAS-PD)¹² to measure of QOL and symptom burden respectively. We chose these scales for their applicability to patients with advanced disease, ease of use with cognitive impairment, brevity and caregiver proxy reporting. More commonly used PD quality of life outcomes (e.g. the Parkinson's Disease Questionnaire 39⁴⁰) are less relevant to the needs of the population we are serving as they focus primarily on functional activities, many of which are beyond the abilities of our patients.

PRELIMINARY DATA AND FEASIBILITY

- 1) Effectiveness of Outpatient Palliative Care for PD: [name] (University of Alberta site PI) and colleagues published a case series of 109 PD patients who had received outpatient palliative care from her team.²⁷ This study showed a significant improvement in symptom burden as measured by the Edmonton Symptom Assessment Scale PD (ESAS-PD) between their baseline (mean \pm STD = 56 \pm 19) and first follow-up visit (40 \pm 17; paired t-test p < 0.0001). Significant improvements were seen in many individual symptoms including pain, anxiety, drowsiness and dysphagia. Although there was no control group, these patients were largely referred by their treating neurologist because of limited success with usual care. Further findings from an article in press by [name] and [name] (PI) showed that over 80% of PD patients participating

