Rationale and Design: There is a growing interest in the economics of healthcare delivery and palliative care.⁷⁴ While there are clear motivations for examining this from a payer and systems perspective, there is also an emerging interest in understanding this from patient and caregiver perspectives.⁷⁵ This also agrees with our qualitative interviews of PD patients and caregivers where one of the most frequent concerns regarding their present situation and the future was finances. The types of services provided for a given cost are also clearly important. For example, one of the services our palliative care clinics provide patients is setting up home care for physical therapy which benefits both patients and caregivers. Our objectives for this Aim are therefore to describe how the addition of outpatient palliative care may alter costs and services for patients and caregivers and also to assess whether recommendations of the palliative care team are implemented and maintained.

Participants: Participants will be identical to Aim 1. Data will be collected from patient-caregiver dyads through interviews and rater-administered questionnaires using items drawn from existing instruments modified to account for PD and the cognitive functioning of dyads. These may be performed by phone within a week of scheduled visits depending on patient/caregiver preferences to minimize fatigue and burden or in person visits.

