Economic Outcomes: From the patient and caregiver perspective there are two key economic outcomes that affect their financial health: out-of-pocket costs for healthcare and non-medical costs resulting from changes in work behaviors and earnings. From a payer and systems perspective the total cost of care is the economic outcome of interest. These economic outcomes will be assessed at baseline and every 6 weeks during the course of the study via modified versions of items drawn from existing questionnaires that have been used with similar populations which may be administered in person or by telephone. Out-of-pocket health-related costs will be assessed using questions drawn from the *Ambulatory and Home Care Record (AHCR)* and the *Medical Expenditure Panel Survey (MEPS)*. Measures of total cost of care will be derived from comprehensive service utilization questions described below including both public and private costs.⁷⁶ Costs will be assigned uniformly for purchased services regardless of patients' underlying insurance status or location using Medicare reimbursement rates for the Denver Metropolitan Area. For services not covered by Medicare (e.g. unskilled home care) we will use average rates for the Denver Metropolitan Area. Measures of work behaviors and earnings will be obtained from questionnaire items adapted from the *Work Productivity and Activity Impairment Questionnaire (WPAI)* and the *World Health Organization Health and Work Performance Questionnaire (HPQ)*. Measures at baseline and follow up will include work activities in the week prior to the assessment, absences from work due to health issues or caregiving and, for caregivers only, the number of hours spent providing care. At baseline we will obtain detailed information on the patient's and caregiver's current or most recent job including usual weekly hours worked, earnings, industry, and occupation. This baseline information will be used to value work absences due to caregiving activities and caregiver's health, time providing care for caregivers, and any patient absences from work. Time losses from work will be assigned a monetary value using the human capital approach with adjustments made by year for inflation (will use dollar value of final year of data collection), vacations and benefits.⁷⁷ Caregiver time spent providing care will be valued using the human capital approach for caregivers that are employed at baseline and for those not employed at baseline we will value their time using local market wage rates for paid home health aides.

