
Service Utilization: Health care utilization data will be collected at baseline, and every 6 weeks along with the economic outcome assessments including information on caregiver and patient use of healthcare services (i.e. emergency room services, hospitalizations, hospice and palliative care services, respite care and other stays in long-term care facilities, home health services, and caregivers' use of psychological health services) as well as outpatient visits to physicians or other services. We will also record place of service (e.g. home, community, tertiary center) and number of medications taken. Utilization measures will use items from the AHCR, MEPS and HPQ.

Statistical Analyses: To estimate economic outcomes, all costs will be aggregated for each 6 week period and expressed as a rate per 30 days (monthly costs). Our primary economic comparison will be for total care costs plus non-medical costs in the period preceding the 6-month visit using a mixed regression model with adjustments made for site, baseline costs and work behaviors of the caregiver. Secondary economic models will examine differences by specific source of cost (e.g. missed work, informal caregiving, direct healthcare costs) and will use linear regression analyses to determine whether patient or caregiver variables (e.g. gender, age, cognitive status) are predictive of costs under either interventions. We will also conduct sensitivity analyses of these cost measures (e.g., measuring cost of missed work and informal caregiving time using both a human capital approach and local wages of home health aides for caregivers not employed at baseline).

Our primary service utilization analysis will compare number of hospitalizations, emergency room visits and nursing home placement between groups. T-tests and regression analyses will be used for continuous outcomes, Poisson regression will be used for count outcomes, and chi-square association tests, Fisher's exact association tests, and logistic regression will be used for binary outcomes. Secondary analyses will examine utilization and place of service for ancillary therapies (e.g. physical, occupational and speech therapy). We will use regression models to determine if total number of medications is associated with QOL and ZBI (as it was in our Preliminary data) and whether palliative intervention influences medication use.

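### Aim 2's primary cost outcome is stated inconsistently: patient and caregiver cost over months 0 to 6 in the Specific Aims, but total care plus non-medical cost over a period of unstated length in the analysis section

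*Combined protocol and SAP*

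**What the plan says.** **Specific Aims, Aim 2.** The primary is defined in one sentence: "Our primary outcome will be the difference between groups in total patients and caregiver costs from month 0 to month 6". The wider view is left to a second tier of analyses, which are to "examine changes in healthcare utilization and cost from a systems perspective". The prediction is that "patient/caregiver costs will be lower for the palliative care group versus usual care at 6 months". Cost and service data are described as covering a look-back "for the three months prior to each study visit".

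**Innovation (item 3) and Aim 2 Rationale and Design.** Both frame the aim around patients and caregivers: "Describe the impact of outpatient palliative care on cost and service utilization from a patient and caregiver perspective", and "describe how the addition of outpatient palliative care may alter costs and services for patients and caregivers".

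**Aim 2 Economic Outcomes.** The patient and caregiver outcomes are "out-of-pocket costs for healthcare and non-medical costs resulting from changes in work behaviors and earnings". Total cost of care, public and private, is named as the outcome for the payer and systems perspective. Collection is at baseline and every 6 weeks.

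**Aim 2 Statistical Analyses.** Costs are aggregated by 6-week period and expressed per 30 days. The next sentence reads: "Our primary economic comparison will be for total care costs plus non-medical costs in the period preceding the 6-month visit". The model is a mixed regression adjusted for site, baseline costs and caregiver work behaviors.

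**Aim 2 Sample Size and Power Calculations.** All figures use 125 per group and alpha 0.05. A two-sample t-test has 90% power at 0.42 SD. A longitudinal contrast in mean total cost has 90% power at 1.75 sd*months over 6 months (0.29 SD on average), and the effect given for 12 months is 3 sd*months (0.25 SD). The SD is in cost per month, under compound symmetry with correlation 0.5. A Poisson count outcome has 90% power at a rate ratio of 0.53 from a control rate of 0.5 per person-year.

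**The concern.** The two statements of the primary differ in what is counted. Total care cost includes amounts borne by payers that patients and caregivers never pay. Insurer-paid hospital cost could fall while out-of-pocket cost rises, so a result on the analysis section's outcome would not answer the question in the Specific Aims.

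The time window is also unsettled. The Specific Aims give months 0 to 6. The analysis section gives a period with no length, directly after a sentence about 6-week periods. The Specific Aims also mention a three-month look-back.

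With more than one candidate primary in the text, the choice could be made after the data are seen. That matters more in a trial the protocol says cannot truly be blinded (Potential Problems and Alternative Strategies, item 5). The window also determines which of the stated power figures applies.

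**Working it through.** **1. Components, side by side**

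| Section | What is primary | Where systems cost sits |
|---|---|---|
| Specific Aims, Aim 2 | Patient and caregiver cost, months 0 to 6 | Secondary |
| Economic Outcomes | (defines terms) patient/caregiver = out-of-pocket + non-medical | Total cost of care = payer/systems |
| Statistical Analyses | Total care + non-medical cost, period before the 6-month visit | Inside the primary |

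By the plan's own definitions, the last row puts a systems-perspective quantity into the primary.

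**2. Reproducing the longitudinal cost power**

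Inputs from the power section: n = 125 per group, 90% power, alpha 0.05, compound symmetry, rho = 0.5. Assumed: two-sided alpha, and adjustment for baseline cost (the analysis section adjusts for it; the power section does not mention it).

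For the mean of m post-baseline periods given baseline, in units of one period's SD squared:

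Var = (1 + (m − 1)·rho)/m − rho²

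Detectable mean difference = (1.960 + 1.282) × √(2/125) × √Var = 0.410 × √Var. Multiply by the months covered to get sd*months.

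- Two quarters: Var = 0.75 − 0.25 = 0.50; 0.410 × 0.707 = 0.290 SD; × 6 = **1.74** (stated 1.75).
- Four quarters: Var = 0.625 − 0.25 = 0.375; 0.410 × 0.612 = 0.251 SD; × 12 = **3.01** (stated 3).
- Four 6-week periods over 6 months: Var = 0.375; 0.251 SD; × 6 = **1.51**.
- Eight 6-week periods over 12 months: Var = 0.5625 − 0.25 = 0.3125; 0.229 SD; × 12 = **2.75**.
- Without baseline adjustment, or as change from baseline (identical at rho 0.5): quarters 2.13 and 3.89; 6-week periods 1.94 and 3.69.
- Monthly periods, baseline-adjusted: 1.42 and 2.66.

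Of these layouts, only quarterly, baseline-adjusted periods reproduce both stated figures. That layout is inferred; the plan does not state it. It fits the three-month look-back in the Specific Aims, not the 6-week periods of the analysis section.

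**3. A single period (m = 1)**

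- Baseline-adjusted: SE = √(0.75) × √(2/125) = 0.1095. Power at 0.29 SD = Φ(0.29/0.1095 − 1.96) = **75%** (67% to 89% for assumed rho 0.3 to 0.7). The 90% detectable effect is 0.355 SD.
- Unadjusted: SE = 0.1265. Power = Φ(0.29/0.1265 − 1.96) = **63%**. The 90% detectable effect is 0.41 SD.

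Here 0.29 is in SDs of that period's own monthly rate. If it means SDs of a three-month rate, it equals 0.29 × √((1 + 0.5)/2) = 0.251 SD of a 6-week rate. One 6-week period, baseline-adjusted, then also has about 63% power.

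**4. The t-test figure**

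With 125 per group and 0.42 SD, the noncentral t gives 91.1% power; the exact 90% detectable effect is 0.412 SD. The stated figure reproduces and needs no accumulation over time.

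**5. The Poisson figure (separate)**

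Rates are 0.5 and 0.53 × 0.5 = 0.265 per person-year, one year, 125 per group: expected events 62.5 and 33.1.

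- Normal approximation on the rate difference: 0.235/√((0.5 + 0.265)/125) = 3.00; Φ(3.00 − 1.96) = 85%.
- Simulation (1,000,000 trials): 85.5% (Wald) and 86.0% (score or likelihood ratio). A rate ratio of 0.50 gives 90.2% to 90.6%.
- A formula with null variance at the control rate: (0.635 − 1.96 × 0.179)/0.215 = 1.32, so 90.7%. This matches the stated 90% but is optimistic.

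**The case against.** Several stronger readings are tempting, and the documents do not support them.

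- *That the stated power fits only a cumulative outcome.* It does not. The t-test at 0.42 SD covers a single-period comparison, and with baseline adjustment at rho 0.5 a single period has about 97% power at that effect. Only the longitudinal figure is tied to the cumulative contrast. The plan never pairs 0.29 SD with a single period.
- *That the two windows flatly contradict each other.* The period before the 6-month visit is given no length, and a mixed model suits several 6-week rates per person. It can be read as all of months 0 to 6. This is ambiguity, though the preceding sentence favours one 6-week period.
- *That 1.75 and 3 sd*months are errors.* They are right for quarterly, baseline-adjusted periods. With 6-week periods and the effect in 6-week SD units, power at 1.75 sd*months would be 96.5%. Nothing here shows the cumulative comparison to be underpowered. The figures need a label.

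It can also be said that Aim 2 is descriptive, that the trial's main outcomes are the QOL-AD and ZBI, that secondary models already split cost by source, and that the operative analysis section may be the intended one. The power section does speak of mean total cost, but in SD units that do not identify the components. All this limits the consequence. It does not remove the mismatch in components: reading the Specific Aims' primary as all costs fails because that paragraph puts the systems perspective in secondary analyses.

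**Conclusion.** The inconsistency in cost components and perspective is firm and rests on the text alone. Following the analysis section would not test the prediction made for Aim 2. The undefined window is a real ambiguity.

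The consequence for power depends on the window. The longitudinal figure holds for a cumulative six-month contrast, matching the Specific Aims' window. Carried to a single period, 0.29 SD has about 75% power adjusted or 63% unadjusted, and 90% then needs about 0.355 or 0.41 SD. These results assume two-sided alpha, compound symmetry, rho 0.5 and 125 per group; the quarterly layout is an inference from the figures.

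The Poisson shortfall, about 4 points, is a separate and minor matter. The point should be corrected, but it concerns the primary outcome of one aim, not the trial's main outcomes.

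**What to change.** 1. **Reconcile the Specific Aims, Economic Outcomes and Statistical Analyses to one primary before the data are seen.** The version that fits the Specific Aims, Innovation and Aim 2 rationale would read, in the analysis section: *The primary economic outcome is patient and caregiver cost (out-of-pocket health-related cost plus non-medical cost, including caregiver time) over months 0 to 6. It is estimated as the between-group difference in average monthly rate across the 6-week periods up to the 6-month visit, from the mixed model adjusted for site, baseline costs and caregiver work behaviors. Total care cost is secondary.* If the sponsor intends total care cost as primary, the Specific Aims and their prediction must change instead, and the window must still be stated.
2. **State the period length behind the SD in the power section.** Either label 1.75 and 3 sd*months as based on quarterly, baseline-adjusted periods, or restate them for 6-week periods: about 1.51 and 2.75 sd*months (0.25 and 0.23 SD on average) at rho 0.5.
3. **Separately, restate the Poisson figure:** about 86% power at a rate ratio of 0.53, with about 0.50 needed for 90%.

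The cost is wording only. The 6-week cost data are already planned, so no participants, visits or measures are added.

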We will recruit PD patients over age 40 diagnosed with probable PD using UK Brain Bank Criteria⁴⁶ or atypical parkinsonian disorders (APD) who are identified to have high potential for palliative care needs using the Palliative Care Needs Assessment Tool.³⁸ When present their family caregivers will also be included. We plan to recruit a total of 300 PD patients and project that at least 80% will have family caregivers who will also be included in this study.

We will *select* participants using the following inclusion and exclusion criteria described above.

PD patients with dementia (PDD) may be considered a vulnerable population but are necessary to answering our research questions. For all patients with cognitive impairment we will formally assess capacity to consent using the University of California Brief Assessment of Capacity to Consent (UBACC) modified for our specific study design where needed.⁸³ For patients who fail this screen or if investigators have additional concerns we will require that their guardian participate in the consenting process and sign an informed consent. We will also require that PDD subjects give consent, or at minimum assent if fully informed consent is not possible. Our protocol and consent forms will be approved by our local IRBs before approaching any potential subjects.

Caregivers will be consented and enrolled using a caregiver-specific consent form.

After enrollment, screening and consent, patients will be randomized in a 1:1 ratio to either usual care or an usual care supplemented by an outpatient interdisciplinary clinic. The interdisciplinary team will consist of a neurologist with palliative care experience, a nurse, social worker, and a chaplain. For the usual care arm, patients not currently seeing a neurologist randomized to this arm have appointments with a neurologist

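### The primary cost model adjusts for caregiver work behaviours, which do not exist for the 10% to 20% of patients without a caregiver, and it leaves out caregiver presence

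*Combined protocol and SAP*

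**What the plan says.** **Outcome.** Aim 2, Statistical Analyses: "Our primary economic comparison will be for total care costs plus non-medical costs in the period preceding the 6-month visit". Aim 2, Economic Outcomes describes "non-medical costs resulting from changes in work behaviors and earnings". Work absences and caregiver hours are both given a money value there: "This baseline information will be used to value work absences due to caregiving activities", and "Caregiver time spent providing care will be valued using the human capital approach for caregivers that are employed at baseline". For caregivers not employed at baseline, time is priced at the local wage of home health aides.

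**Covariates.** The model is fitted "with adjustments made for site, baseline costs and work behaviors of the caregiver". Economic Outcomes collects work data at more than one time: "Measures at baseline and follow up will include work activities in the week prior to the assessment".

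**Population.** Aim 2, Participants takes over the Aim 1 participants unchanged, though it describes data collection in terms of dyads. Under Aim 1 a caregiver is enrolled only where there is one (Study Settings/Recruitment), and randomisation is stratified by site, caregiver presence and dementia (Randomization). The expected share with a caregiver is 90% in Aim 1, Participants. In Human Subjects 1.a the investigators "project that at least 80% will have family caregivers".

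**Missing covariates.** The only rule is in Aim 1, Statistical Analysis: the initial likelihood analysis uses the available outcome data of those for whom every explanatory variable is observed. Aim 2 has no rule of its own.

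**The concern.** A regression needs a value of each covariate for each patient. Caregiver work behaviour has none when there is no caregiver, and this is a planned part of the sample rather than an accident of data collection. The plan does not say whether such a patient is coded as zero, given a separate category or left out. The choice decides who is in the primary cost comparison.

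Caregiver presence should bear strongly on the outcome, because caregiver hours and missed work are priced into it, and it is a stratification factor. Yet of the stratification factors, only site is named in the cost model.

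The second, smaller issue is timing. The term work behaviours names both an input to the outcome and a covariate, and it is measured before and after randomisation. A post-randomisation value as covariate would absorb part of the effect being estimated.

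**Working it through.** **1. Patients affected.** 10% to 20% of 300 randomised is 30 to 60. Of the 250 evaluable patients behind the power statement (125 per group), it is 25 to 50. That leaves 125 × 0.9 = 112.5 or 125 × 0.8 = 100 per group. The share is assumed to be the same in both arms, as stratification implies, and the same among evaluable as among randomised patients.

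**2. Reproducing the plan's figure.** Aim 2, Sample Size and Power Calculations gives 1.75 sd·months (0.29 SD on average) over 6 months, with 125 per group, 90% power, alpha 0.05, compound symmetry and correlation 0.5. Two-sided testing is assumed. For the mean of k follow-up periods adjusted for baseline:

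- variance V = (1 + (k − 1)ρ)/k − ρ²
- detectable difference = (1.960 + 1.282) × √(2V/n)

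With two 3-month periods, V = 1.5/2 − 0.25 = 0.5, so the difference is 3.242 × √(1/125) = 0.290 SD, or 1.74 sd·months. With four 3-month periods over 12 months, V = 0.375, giving 0.251 SD or 3.01 sd·months, against the stated 0.25 and 3. Without baseline adjustment the 6-month value would be 0.355 SD; with 6-week periods it would be 0.251 SD. Neither matches 0.29. The stated figure therefore reproduces with all 125 per group and baseline adjustment.

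**3. If patients without a caregiver drop out.** With V = 0.5, power at 0.29 SD is Φ(0.29 × √n − 1.960).

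| Without caregiver | n per group | Detectable difference | Power at 0.29 SD |
|---|---|---|---|
| 0% (as planned) | 125 | 0.290 SD (1.74 sd·months) | Φ(1.28) = 90.0% |
| 10% | 112.5 | 0.306 SD (1.83 sd·months) | Φ(1.12) = 86.8% |
| 20% | 100 | 0.324 SD (1.94 sd·months) | Φ(0.94) = 82.6% |

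The relative loss does not depend on V: √(1/0.9) = 1.054 and √(1/0.8) = 1.118, so 5% to 12%. For the plan's simple t-test at 0.42 SD, power goes from 91.1% (stated as 90%) to 88.0% or 84.0%. These figures assume the same SD among patients with a caregiver as in the whole sample.

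**4. Timing of work behaviours.** In the covariate phrase, the word baseline can govern costs alone or both nouns. No section places a follow-up work measure in the primary cost model. If one were used, the estimate would shrink towards zero by roughly the part of the effect that acts through caregiver work. The documents give no figure for that part, so the size cannot be computed.

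**The case against.** The strongest reply is that the plan, read sensibly, already does the right thing.

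- **Timing.** Aim 1 speaks of baseline confounders and baseline depression, detailed job data are taken at baseline, and caregivers are classed by employment at baseline. Time-varying covariates are mentioned only for secondary Aim 1 analyses of crossover. This stands: baseline is the natural reading. A reader might infer that the plan adjusts away part of its own outcome; the documents do not say so.
- **Exclusion.** The complete-covariate rule belongs to Aim 1 and deals with missing data. Aim 2 keeps the Aim 1 participants and powers cost on 125 per group, whereas the ZBI calculation is cut to 110 or 90 dyads. The investigators thus seem to intend to keep everyone. This also stands, so exclusion is a conditional consequence, not a stated plan. But the intention needs a coding rule, and there is none. Zero is a natural value, yet zero alone would put a patient without a caregiver level with one whose caregiver does not work, although that caregiver's time is costed. Hence the need for a presence term.
- **Intention to treat.** A reader might infer that losing these patients breaks the randomised comparison. It does not: presence is a pre-randomisation stratum, so those who remain are still compared as randomised. The loss is in coverage and precision.
- **Mechanism.** A reader might take missed work to be a main route of the expected savings. The Specific Aims predict lower patient and caregiver costs and a move from acute care to home services; they do not single out missed work.
- **Importance.** Aim 2 is framed as descriptive, and no stated figure is wrong. This limits the weight of the point but does not remove it.

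**Conclusion.** The point holds as a specification gap with a definite consequence. On either reading of the timing, the covariate is undefined for 10% to at most 20% of patients, no rule says how they enter the model, and caregiver presence is missing from it.

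If the Aim 1 rule is carried over, the primary cost comparison covers only patients with a caregiver, contrary to Aim 2, Participants. The loss of precision in the table above is moderate. It rests on that carry-over, on two-sided testing and on the plan's own covariance assumptions. If everyone is kept under a stated coding, the planned 90% is restored.

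The timing of work behaviours is an ambiguity to close, not a demonstrated over-adjustment. The QOL-AD and ZBI primary outcomes are not affected.

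**What to change.** In Aim 2, Statistical Analyses, replace the covariate list with: site, baseline costs, caregiver presence (yes or no), and caregiver work status and usual weekly hours at baseline, both set to zero where there is no caregiver. Add that all participants are kept in the primary cost model and that no follow-up work measure is a covariate in it.

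The baseline job questions cover the current or most recent job, so the definition should also say that hours refer to work held at baseline.

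The cost is a sentence or two. Caregiver presence is known at randomisation and the job data are already taken at baseline. No new data are needed and the sample size does not change.
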